### 14.2.2. Reporting

The investigators will report all SAEs and DDs to the sponsor, immediately but not later than 3 calendar days after investigation site study personnel's awareness of the event. This includes detected errors at defibrillator self-test after each use.

The sponsor will report to the Swedish Medical Products Agency all of the following reportable events:

- any SAE that has a causal relationship with the investigational device, the comparator
  or the investigation procedure, or where such causal relationship is reasonably
  possible;
- any DD that might have led to a SAE if appropriate action had not been taken, intervention had not occurred, or circumstances had been less fortunate; and
- any new findings in relation to any event referred to above.

Reporting by the sponsor will be done by filling out the "Summary Reporting Form" (MDCG 2020-10/2). The form will be filled in/updated for each reportable event or for new findings/updates to already reported events. The form will be transmitted to the Swedish Medical Products Agency. For events that indicate an imminent risk of death, serious injury, or serious illness and that requires prompt remedial action for other patients/subjects, users or other persons or a new finding to it will be reported immediately, but not later than 2 calendar days after awareness by sponsor of a new reportable event or of new information in relation with an already reported event. Any other reportable events or a new finding/update

Version No: 1.1

Date: 2024-10-27 42 (48)

to it will be reported immediately, but not later than 7 calendar days following the date of awareness by the sponsor of the new reportable event or of new information in relation with an already reported event.

## 14.2.3. **Assessment of Causality**

The relationship between each adverse event and the investigational device, the comparator and the investigation procedure will be assessed and recorded by the investigator and sponsor.

The sponsor and investigator will distinguish between SAEs related to the investigational device and those related to the procedures, relatedness to both is possible. Each SAE will be classified according to four different levels of causality:

#### 1. Not related

Relationship to the device, comparator or procedures can be excluded when:

- the SAE can be attributed to another cause (e.g. an underlying or concurrent illness/ clinical condition, an effect of another device, drug, treatment or other risk factors);
- the event has no temporal relationship with the use of the investigational device, or the procedures related to application of the investigational device;
- the SAE does not follow a known response pattern to the medical device (if the response pattern is previously known) and is biologically implausible;
- the discontinuation of medical device application or the reduction of the level of activation/exposure - when clinically feasible - and reintroduction of its use (or increase of the level of activation/exposure), do not impact on the serious adverse event;
- the event involves a body-site or an organ that cannot be affected by the device or procedure;

In order to establish the non-relatedness, not all the criteria listed above might be met at the same time, depending on the type of device/procedures and the SAE.

#### 2. Possible

The relationship with the use of the investigational device or comparator, or the relationship with procedures, is weak but cannot be ruled out completely. Alternative causes are also possible (e.g. an underlying or concurrent illness/ clinical condition or/and an effect of another device, drug or treatment). Cases where relatedness cannot be assessed, or no information has been obtained shall also be classified as possible.

#### 3. Probable

The relationship with the use of the investigational device or comparator, or the relationship with procedures, seems relevant and/or the event cannot be reasonably explained by another cause.

Version No: 1.1

Date: 2024-10-27 43 (48)

#### 4. Causal relationship

The SAE is associated with the investigational device, comparator or with procedures beyond reasonable doubt when:

- the event is a known side effect of the product category the device belongs to or of similar devices and procedures;
- the event has a temporal relationship with investigational device use/application or procedures;
- the event involves a body-site or organ that
  - o the investigational device or procedures are applied to;
  - o the investigational device or procedures have an effect on;
- the serious adverse event follows a known response pattern to the medical device (if the response pattern is previously known);
- other possible causes (e.g. an underlying or concurrent illness/ clinical condition or/and an effect of another device, drug or treatment) have been adequately ruled out;
- harm to the subject is due to error in use;

In order to establish the relatedness, not all the criteria listed above might be met at the same time, depending on the type of the SAE.

#### 14.3. List of foreseeable Adverse events

- 1. Compromised CPR-quality. There is a risk that application of a second defibrillator will be associated with interruptions in CPR-quality. Short interruptions are judged to be of no or less significance since they allow for an intervention with a potentially life-saving treatment. However, long interruptions in chest compressions might have an adverse impact on outcome. All interruption > 60s in the intervention-group detected at CRP-quality evaluation will be considered as an probable AE and the monitor / sponsor will be notified and actions taken in accordance with the monitoring plan.
- 2. Device deficiency. The inability of one of the defibrillators to deliver energy at defibrillation or shut down / reboot. This risk is judged to be exceedingly low based on the preclinical testing and the results from the previous trials (likely incidence < 1/100). However, it's impossible to rule out. Defibrillation data will be analyzed for each case and inability to defibrillate will be considered as a SADE. All defibrillator files will be analyzed for energy delivery at each defibrillation.

Perceived adverse event by participating EMS-units will also be collected in CRF1. All CRF1 forms with perceived adverse events will be followed up by the sponsor with undue delay, the monitor will be informed and the type of adverse event and it's relationship with the intervention or the investigational device will be judged according to definitions in the CIP.

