#### A. For all patients after finished resuscitation:

- Prehospital Digital CRF 1 (see below)
- Swedish Register of Cardiopulmonary Resuscitation (SRCR) part 1, pre-hospital treatment, patient characteristics and short-term outcome
- ECG files from corpuls3 used by including ambulance unit
- Ambulance charts
- EMS emergency dispatch organization time delays (from the Swedish emergency dispatch organization SOS-Alarm)

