#### 8.1 Prehospital CRF1, Characteristics during the resuscitation phase

After completing the care of the patient, the study responsible EMS-unit will report a digital prehospital CRF. This is practically done by using and reading a study specific QR-code located on the back of the specific randomization envelope / sheet using a smart-phone. This will open a webpage automatic registration of time of registration and information to be filled in when opened.

Version No: 1.1

Date: 2024-10-27 33 (48)

The prehospital CRF will contain basic on-site information such as which ambulance that performed randomization, randomization study number, time and date of cardiac arrest, number of shocks prior to EMS arrival and number of shocks prior to randomization, treatment allocation, electrode placement for each defibrillation, number of defibrillations before DSD, ROSC and if the patients survived the event. Furthermore, if the patient has a known identity, personal id-number will be included to enable follow up. If the patients do not have a known identity a temporary identification number will be used.

The prehospital CRF allows for real-time monitoring of randomization and allows for early start of follow-up.

Other core resuscitation characteristics will later be reported and collected from the SRCR part 1 and ambulance charts. This registry data is standard and mandatory for all EMS personal to report and contains resuscitation and patient characteristics and reporting to the register is part of routine documentation.

ECG files from defibrillators. All data stored in the defibrillators after each use in the trial will be exported to a secure server and analyzed for defibrillation safety and CPR quality.

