#### 14.1.1. Adverse Event

An Adverse Event (AE) is untoward medical occurrence, unintended disease or injury or any untoward clinical signs, including an abnormal laboratory finding, in subjects, users or other persons, in the context of a clinical investigation, whether or not related to the investigational device.

This definition includes events that are anticipated as well as unanticipated events. This definition includes events occurring in the context of a clinical investigation related to the investigational device, the comparator or the procedures involved.

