#### 14.1.2. Adverse Device Effect

An Adverse Device Effect (ADE) is any AE related to the use of an investigational medical device.

This definition includes adverse events resulting from insufficient or inadequate instructions for use, deployment, implantation, installation, or operation, or any malfunction of the investigational medical device.

This definition includes any event resulting from use error or from intentional misuse of the investigational medical device. This includes both the interventional and comparator.

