## 14.2. Recording and Reporting

#### 14.2.1. Recording

The principal investigator or an authorized designee will record:

- all AEs except the events specified not to be recorded
- all SAEs;
- all DDs;
- - any new finding in relation to any of the above-mentioned events.

Events that are related to cardiac arrest and would be expected in patients undergoing attempted resuscitation should NOT be reported. These include:

- Death
- Hospitalization
- Persistent or significant disability or incapacity
- Organ failure

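### Section 14.3 flags chest-compression pauses over 60 s automatically as probable AEs in the intervention group only, so any AE listing that includes them is ascertained unequally by arm

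*Protocol*

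**What the plan says.** Item 1 of protocol section 14.3 names compromised CPR quality from applying a second defibrillator as a foreseeable adverse event. It then sets the rule: "All interruption > 60s in the intervention-group detected at CRP-quality evaluation will be considered as an probable AE". The monitor or sponsor is notified and acts under the monitoring plan. The section gives no corresponding rule for the control group.

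The data behind the rule are not limited by arm. Section 8.1 A lists, for all patients, "ECG files from corpuls3 used by including ambulance unit". The prehospital CRF1 section adds that the device recordings "after each use in the trial will be exported to a secure server and analyzed for defibrillation safety and CPR quality".

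The AE framework also covers both arms:
- 14.1.1, on AEs: "This definition includes events occurring in the context of a clinical investigation related to the investigational device, the comparator or the procedures involved".
- 14.1.2, on adverse device effects: "This includes both the interventional and comparator".
- 14.2.1 requires the recording of "all AEs except the events specified not to be recorded".
- 14.2.3: "The relationship between each adverse event and the investigational device, the comparator and the investigation procedure will be assessed and recorded".

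Two further routes into the record exist. Section 14.3 says "Perceived adverse event by participating EMS-units will also be collected in CRF1", and section 4.5 provides for case-by-case monitoring with individual assessment for every included patient.

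**The concern.** The same event, found in the same kind of file at the same review, is handled differently according to the randomised arm. In a DSD patient, a pause over 60 s becomes a probable AE and triggers a notice without further judgement. In a control patient, someone must first decide that it is an AE, or the crew must have perceived and reported it. Crews know the allocation (6.4 and 6.5).

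Safety in terms of CPR quality is a stated objective of the pilot, and its results are meant to inform a larger trial. If an AE table or listing includes these pauses, some of the apparent excess under DSD could come from the recording rule and not from the treatment.

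**Working it through.** The protocol states no figure that can be reproduced here. The check is first one of wording, then an illustration of size.

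**1. Which pauses the automatic rule covers.** The motive in 14.3 is the application of a second defibrillator. The rule itself is wider: it covers every pause over 60 s in the arm, not only those at pad placement. A pause with a cause common to both arms is therefore flagged under DSD and not flagged under control.

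**2. Routes into the AE record.**

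| Route | DSD | Control |
|---|---|---|
| Automatic > 60 s flag with notice (14.3) | yes | not stated |
| General duty to record AEs (14.2.1) | yes | yes |
| Crew-perceived event on CRF1 (14.3) | yes | yes |
| Case-by-case assessment of included patients (4.5) | yes | yes |

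The last three routes are open to both arms, so they do not offset the first. They do reduce the number of control pauses that would be missed.

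**3. Illustration of size.**
- From 6.3.3: 30 patients randomised to DSD and 10 to standard treatment.
- Assumed, because the protocol gives neither: p, the true proportion of patients with a pause over 60 s, equal in both arms; and c, the share of control pauses caught by the other routes.
- Expected DSD patients flagged = 30p. Expected control patients with such a pause = 10p. Control patients missing from the record = 10p(1 − c). Spurious risk difference = p − pc = p(1 − c).

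| p | DSD flagged, 30p | Control with pause, 10p | Control missing at c = 0 / 0.5 / 1 | Spurious difference at c = 0 / 0.5 / 1 (points) |
|---|---|---|---|---|
| 5% | 1.5 | 0.5 | 0.5 / 0.25 / 0 | 5 / 2.5 / 0 |
| 10% | 3 | 1 | 1 / 0.5 / 0 | 10 / 5 / 0 |
| 20% | 6 | 2 | 2 / 1 / 0 | 20 / 10 / 0 |

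The chance that at least one of 10 controls has such a pause is 1 − (1 − p)^10, which is 40%, 65% and 89% at p = 5%, 10% and 20%. At a lower assumed p of 1% to 2%, only 0.1 to 0.2 control patients are expected, and the chance of none is 0.99^10 = 90% to 0.98^10 = 82%.

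**4. What a reader of the results would see.** Take p = 10% and the extreme c = 0. The record shows 3/30 against 0/10, a difference of +10 points (Newcombe 95% CI −18.5 to +25.6). With equal recording it would show 3/30 against 1/10, a difference of 0 points (−31.1 to +17.6). Both intervals include 0, so the distortion lies in the listing and the point estimate and would not produce a firm conclusion.

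**The case against.** The limit to one arm has a stated reason. The item describes a risk from a second defibrillator, controls do not have one, and the sentence serves to alert the monitor or sponsor; it does not define an endpoint. That explains the focus on DSD. It does not make the recorded counts comparable, because the rule reaches pauses unrelated to pad placement.

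Three stronger readings are tempting, and the document does not support them.

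- **Control pauses are never recorded.** A reader might infer this from 14.3 alone. The general AE duty, CRF1 and the case-by-case assessment in 4.5 all remain open, so c = 0 is an extreme and not the expected state. Section 4.5 could be read narrowly as feedback on the study intervention, but it speaks of every included patient.
- **A primary safety endpoint is biased.** Section 6.2.1 gives device deficiency and skin burns as examples of major adverse events, not pauses. Compression fraction has a target in both groups and does not depend on the 14.3 rule. Section 7.4 says that no hypothesis testing will be performed.
- **Pauses under DSD cannot be put in context.** The control files are collected and analysed anyway, so a control count could be produced from data already held. Only the automatic label and notice are missing.

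Three other points also stand. The monitoring plan is an appendix that is not shown and may treat control pauses in the same way. The pause rate is wholly assumed. Any distortion runs against DSD, which is the cautious direction for a use partly outside the CE mark. Caution of that kind is a reason to keep the flag for DSD, not a reason to withhold it from controls.

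**Conclusion.** The asymmetry is real and is written into the protocol: automatic classification and notice in one arm, discretionary capture in the other, from files analysed for both. The consequence is limited to the AE listing and to any descriptive AE comparison that includes these pauses.

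The size cannot be determined from the protocol. If the true rate is equal in both arms and lies between 5% and 20%, the trigger passes over 0.5 to 2 expected control patients. The spurious difference lies between 0 (other routes catch every control pause) and 5 to 20 points (they catch none). A lower rate makes it smaller still. Severity: minor, but worth correcting because the correction is cheap.

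**What to change.** In 14.3, item 1, strike the words that limit the rule to the intervention group, so that the existing flag and notice apply to both randomised groups from the same file review. Leave the threshold as it stands. Assess the relation of each flagged pause to the device, the comparator and the procedure case by case under 14.2.3.

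No new data are needed, since the files are already collected and analysed. The cost is a few more AE entries and notices from about 10 control patients (0.5 to 2 expected at the assumed rates) and an amendment to the clinical investigation plan. Under section 9, that amendment needs authority approval before implementation if it is judged substantial.

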#### 14.4. Monitoring

Version No: 1.1

Date: 2024-10-27 44 (48)

Monitoring will be performed by the monitor according to the monitoring plan, please see appendix "Monitoring plan".

## 15. Premature termination of the clinical investigation

The sponsor may suspend or prematurely terminate either the clinical investigation at an individual investigation site or the entire clinical investigation for significant and documented reasons. The Swedish Medical Products Agency may suspend or prematurely terminate the clinical investigation at the applicable investigation sites.

If suspicion of an unacceptable risk to subjects arises during the clinical investigation, or when so instructed by the Medical Products Agency, the sponsor will suspend the clinical investigation while the risk is assessed. The sponsor will terminate the clinical investigation if an unacceptable risk is confirmed. The sponsor will inform all investigators.

The sponsor shall consider terminating or suspending the participation of a particular investigation site or investigator in the clinical investigation if monitoring or auditing identifies serious or repeated deviations on the part of an investigator. If the suspension or premature termination was in the interest of safety, the sponsor shall inform all other principal investigators.

If, in the opinion of the investigator, the clinical observations in the clinical investigation suggest that it may be unsafe to continue the investigation at the site, the investigator may terminate participation in the investigation after consultation with the sponsor. A written statement fully documenting the reasons for such termination will be provided to the sponsor. If the clinical investigation is prematurely terminated, the investigators shall promptly inform the subjects and take necessary steps to finalize their engagement in the clinical investigation. All relevant investigation material must be collected, and accountability completed.

If the clinical investigation is interrupted or terminated prematurely the sponsor will report to the Medical Products Agency within 15 days together with a justification. If the sponsor has temporarily halted or prematurely terminated the clinical investigation on safety grounds, the Medical Products Agency will be informed within 24 hours. A clinical investigation report will be prepared within three months of the early termination or temporary halt, irrespective of the results. In the event that the clinical investigation is restarted within three months of the temporary halt, the sponsor does not have to submit a clinical investigation report until the clinical investigation has been completed.

The final clinical investigation report shall include detail with respect to the temporary halt.

All patients included before the temporal halt or premature termination will be followed up until final planned follow-up after 180 days.

# 16. Publication policy

The clinical investigation will be registered in a publicly accessible database before the start of recruitment activities and the content will be updated throughout the conduct of the clinical

Version No: 1.1

Date: 2024-10-27 45 (48)

investigation and the results entered at completion of the clinical investigation. (www.clinicaltrials.org)

The results of the study will be published in international medical journals after study completion. Criteria for authorship will follow Vancouver guidelines. The PI will have full access to all data and make the final decision to submit for publication.

Version No: 1.1

Date: 2024-10-27 46 (48)

